Figure 5. Individual Subject-overlay Plasma Free 15(S)-HEPE Concentrations (ng/mL) versus Time (linear and semilogarithmic scales) for 1000 mg BD DS102 Administered Orally Twice-daily to Patients with Alcoholic Hepatitis (Protocol DS102A-05-AH1 – Pilot Phase, Trough Concentrations).

Figure 6. Individual Subject-overlay Plasma Total 15(S)-HEPE Concentrations (ng/mL) versus Time (linear and semilogarithmic scales) for 1000 mg BD DS102 Administered Orally Twice-daily to Patients with Alcoholic Hepatitis (Protocol DS102A-05-AH1 – Pilot Phase, Trough Concentrations).

APPENDICES

Appendix Figures 1.1-1.6. Individual Plasma Free 15(S)-HEPE Concentrations (ng/mL) versus Time (semilogarithmic scale only) and Terminal Phase Regressions, by Subject for 1000 mg BD DS102 Administered Orally Twice-daily to Patients with Alcoholic Hepatitis (Protocol DS102A-05-AH1- Pilot Phase, Days 0 and 7).

Appendix Figures 1.7-1.12. Individual Plasma Total 15(S)-HEPE Concentrations (ng/mL) versus Time (semilogarithmic scale only) and Terminal Phase Regressions, by Subject for 1000 mg BD DS102 Administered Orally Twice-daily to Patients with Alcoholic Hepatitis (Protocol DS102A-05-AH1- Pilot Phase, Days 0 and 7).

DATA DISPLAYS FOR TREATMENT STUDY-PHASE (prepared separately)

Table x1. Descriptive Statistics for Plasma Free 15(S)-HEPE Concentrations (ng/mL) for 1000 mg BD DS102 Administered Orally Twice-daily to Patients with Alcoholic Hepatitis (Protocol DS102A-05-AH1 – Treatment Phase).

Table x2. Descriptive Statistics for Plasma Total 15(S)-HEPE Concentrations (ng/mL) for 1000 mg BD DS102 Administered Orally Twice-daily to Patients with Alcoholic Hepatitis (Protocol DS102A-05-AH1 – Treatment Phase).

Table x3. Individual Plasma Free 15(S)-HEPE Concentrations (ng/mL) for 1000 mg BD DS102 Administered Orally Twice-daily to Patients with Alcoholic Hepatitis (Protocol DS102A-05-AH1 – Treatment Phase).

Table x4. Individual Plasma Total 15(S)-HEPE Concentrations (ng/mL) for 1000 mg BD DS102 Administered Orally Twice-daily to Patients with Alcoholic Hepatitis (Protocol DS102A-05-AH1 – Treatment Phase).

Figure x1. Mean (+/-SD) Plasma Free 15(S)-HEPE Concentrations (ng/mL) versus Time (linear and semilogarithmic scales) for 1000 mg BD DS102 Administered Orally Twice-daily to Patients with Alcoholic Hepatitis (Protocol DS102A-05-AH1 – Treatment Phase).

Figure x2. Mean (+/-SD) Plasma Total 15(S)-HEPE Concentrations (ng/mL) versus Time (linear and semilogarithmic scales) for 1000 mg BD DS102 Administered Orally Twice-daily to Patients with Alcoholic Hepatitis (Protocol DS102A-05-AH1 – Treatment Phase).

Figure x3. Individual Subject-overlay Plasma Free 15(S)-HEPE Concentrations (ng/mL) versus Time (linear and semilogarithmic scales) for 1000 mg BD DS102 Administered Orally Twice-daily to Patients with Alcoholic Hepatitis (Protocol DS102A-05-AH1 – Treatment Phase).

Figure x4. Individual Subject-overlay Plasma Total 15(S)-HEPE Concentrations (ng/mL) versus Time (linear and semilogarithmic scales) for 1000 mg BD DS102 Administered Orally Twice-daily to Patients with Alcoholic Hepatitis (Protocol DS102A-05-AH1 – Treatment Phase).

Mock Data Displays

Content and layout of the planned tables and figures are represented in the mock displays (provided separately from this document). Final format and content may differ from these displays depending on the outcome of the data analysis.

PK Mock Data Displays - TABLES
Study DS102A-05-AH1
Pilot and Treatment Phases
PKPDs# Afn091318a

TABLES
In-Text:
Table A

Descriptive Statistics for Plasma Free 15(S)-HEPE Pharmacokinetic Results for 1000 mg BD DS102 Administered Orally Twice-daily to Patients with Alcoholic Hepatitis (Protocol DS102A-05-AH1 – Pilot Phase)

Table B

Descriptive Statistics for Plasma Total 15(S)-HEPE Pharmacokinetic Results for 1000 mg BD DS102 Administered Orally Twice-daily to Patients with Alcoholic Hepatitis (Protocol DS102A-05-AH1 – Pilot Phase)

End-of-Text:
Table 1

Individual Plasma Free 15(S)-HEPE Concentrations (ng/mL) and Descriptive Statistics for 1000 mg BD DS102 Administered Orally Twice-daily to Patients with Alcoholic Hepatitis (Protocol DS102A-05-AH1 – Pilot Phase, Day 0)

Table 2

Individual Plasma Free 15(S)-HEPE Concentrations (ng/mL) and Descriptive Statistics for 1000 mg BD DS102 Administered Orally Twice-daily to Patients with Alcoholic Hepatitis (Protocol DS102A-05-AH1 – Pilot Phase, Day 7)

Table 3

Individual Plasma Free 15(S)-HEPE Concentrations (ng/mL) and Descriptive Statistics for 1000 mg BD DS102 Administered Orally Twice-daily to Patients with Alcoholic Hepatitis (Protocol DS102A-05-AH1 – Pilot Phase, Troughs)

Table 4

Individual Plasma Total 15(S)-HEPE Concentrations (ng/mL) and Descriptive Statistics for 1000 mg BD DS102 Administered Orally Twice-daily to Patients with Alcoholic Hepatitis (Protocol DS102A-05-AH1 – Pilot Phase, Day 0)

Table 5

Individual Plasma Total 15(S)-HEPE Concentrations (ng/mL) and Descriptive Statistics for 1000 mg BD DS102 Administered Orally Twice-daily to Patients with Alcoholic Hepatitis (Protocol DS102A-05-AH1 – Pilot Phase, Day 7)

Table 6

Individual Plasma Total 15(S)-HEPE Concentrations (ng/mL) and Descriptive Statistics for 1000 mg BD DS102 Administered Orally Twice-daily to Patients with Alcoholic Hepatitis (Protocol DS102A-05-AH1 – Pilot Phase, Troughs)

Table 7

Individual Plasma Free 15(S)-HEPE Pharmacokinetic Parameter Values and Descriptive Statistics for 1000 mg BD DS102 Administered Orally Twice-daily to Patients with Alcoholic Hepatitis (Protocol DS102A-05-AH1 – Pilot Phase)

Table 8

Individual Plasma Total 15(S)-HEPE Pharmacokinetic Parameter Values and Descriptive Statistics for 1000 mg BD DS102 Administered Orally Twice-daily to Patients with Alcoholic Hepatitis (Protocol DS102A-05-AH1 – Pilot Phase)

DATA DISPLAYS FOR TREATMENT STUDY-PHASE (prepared separately)

Table x1 Descriptive Statistics for Plasma Free 15(S)-HEPE Concentrations (ng/mL) for 1000 mg BD DS102 Administered Orally Twice-daily to Patients with Alcoholic Hepatitis (Protocol DS102A-05-AH1 – Treatment Phase)

Table x2 Descriptive Statistics for Plasma Total 15(S)-HEPE Concentrations (ng/mL) for 1000 mg BD DS102 Administered Orally Twice-daily to Patients with Alcoholic Hepatitis (Protocol DS102A-05-AH1 – Treatment Phase)

Table x3 Individual Plasma Free 15(S)-HEPE Concentrations (ng/mL) or 1000 mg BD DS102 Administered Orally Twice-daily to Patients with Alcoholic Hepatitis (Protocol DS102A-05-AH1 – Treatment Phase)

Table x4 Individual Plasma Total 15(S)-HEPE Concentrations (ng/mL) and 000 mg BD DS102 Administered Orally Twice-daily to Patients with Alcoholic Hepatitis (Protocol DS102A-05-AH1 – Treatment Phase)

PK Mock Data Displays - TABLES**Study DS102A-05-AH1****Pilot and Treatment Phases****PKDS# Afm091318a**

Note: Parameters shown without subscripting

A	Free
B	Total

Statistic	Pharmacokinetic Parameter					
	tmax	Cmax	AUCt	AUCtau	%Extrap	t ^{1/2}
n						
GeoMean						
Mean						
SD						
CV%						
Minimum						
Median						
Maximum						

Subject	Pharmacokinetic Parameter					
	tmax	Cmax	AUCtau	Cavg	tss	Rac
n						
GeoMean						
Mean						
SD						
CV%						
Minimum						
Median						
Maximum						

PK Mock Data Displays - TABLES
Study DS102A-05-AH1
Pilot and Treatment Phases
PKPDs# Afm091318a

1 Free
4 Total

PK Mock Data Displays - TABLES
Study DS102A-05-AH1
Pilot and Treatment Phases
PKPDs# Afm091318a

2 Free
5 Total

PK Mock Data Displays - TABLES
Study DS102A-05-AH1
Pilot and Treatment Phases
PKPDSS# Afm091318a

3 Free
6 Total

Subject	Day 0, 0 hr	Day 0, 12 hr	Day 3	Day 5	Day 7	Day 14	Day 21	Day 28
1								
2								
3								
4								
5								
6								
	n							
	GeoMean							
	Mean							
	SD							
	CV%							
	Minimum							
	Median							
	Maximum							

PK Mock Data Displays - TABLES
Study DS102A-05-AH1

Pilot and Treatment Phases

PKDS# Afm091318a

Note: Parameters shown without subscripting

Subject	Day 0						Pharmacokinetic Parameter			
	tmax	Cmax	tlast	Clast	AUCt	AUCtau	AUCinf	%Extrap	KeI	t½
1										
2										
3										
4										
5										
6										
n										
GeoMean										
Mean										
SD										
CV%										
Minimum										
Median										
Maximum										

PK Mock Data Displays - TABLES**Study DS102A-05-AH1****Pilot and Treatment Phases****PKDSS# Afm091318a**

Note: Parameters shown without subscripting

Day 7		Pharmacokinetic Parameter										
Subject	tmax	Cmax	tlast	Clast	AUCt	AUCtau	Cavg	tss	Rac	Flucp	Kei	t ^{1/2}
1												
2												
3												
4												
5												
6												
n												
GeoMean												
Mean												
SD												
CV%												
Minimum												
Median												
Maximum												

PK Mock Data Displays - TABLES
Study DS102A-05-AH1
Pilot and Treatment Phases
PKPDSS# Afm091318a

x1 Free
x2 Total

Statistic	Day 0	Day 3	Day 5	Day 7	Day 14	Day 21	Day 28
n							
GeoMean							
Mean							
SD							
CV%							
Minimum							
Median							
Maximum							

PK Mock Data Displays - TABLES
Study DS102A-05-AH1
Pilot and Treatment Phases
PKPDSS# Afm091318a

x3 Free
x4 Total

Subject	Day 0	Day 3	Day 5	Day 7	Day 14	Day 21	Day 28
1							
2							
3							
.
.
.
.
n							

PK Mock Data Displays - FIGURES
Study DS102A-05-AH1
Pilot and Treatment Phases
PKPDsf Affm091318a

In-Text:
Figure A Mean (+/-SD) Day-overlays Plasma Free 15(S)-HEPE Concentrations (ng/ml) versus Time (linear and semilogarithmic scales) for 1000 mg BD DS102 Administered Orally Twice-daily to Patients with Alcoholic Hepatitis (Protocol DS102A-05-AH1 – Pilot Phase, Days 0 and 7)

Figure B Mean (+/-SD) Day-overlays Plasma Total 15(S)-HEPE Concentrations (ng/ml) versus Time (linear and semilogarithmic scales) for 1000 mg BD DS102 Administered Orally Twice-daily to Patients with Alcoholic Hepatitis (Protocol DS102A-05-AH1 – Pilot Phase, Days 0 and 7)

Figure C Mean (+/-SD) Plasma Free 15(S)-HEPE Concentrations (ng/ml) versus Time (linear and semilogarithmic scales) for 1000 mg BD DS102 Administered Orally Twice-daily to Patients with Alcoholic Hepatitis (Protocol DS102A-05-AH1 – Pilot Phase, Trough Concentrations)

Figure D Mean (+/-SD) Plasma Total 15(S)-HEPE Concentrations (ng/ml) versus Time (linear and semilogarithmic scales) for 1000 mg BD DS102 Administered Orally Twice-daily to Patients with Alcoholic Hepatitis (Protocol DS102A-05-AH1 – Pilot Phase, Trough Concentrations)

End-of-Text:
Figure 1 Individual Subject-overlays Plasma Free 15(S)-HEPE Concentrations (ng/ml) versus Time (linear and semilogarithmic scales) for 1000 mg BD DS102 Administered Orally Twice-daily to Patients with Alcoholic Hepatitis (Protocol DS102A-05-AH1 – Pilot Phase, Day 0)

Figure 2 Individual Subject-overlays Plasma Total 15(S)-HEPE Concentrations (ng/ml) versus Time (linear and semilogarithmic scales) for 1000 mg BD DS102 Administered Orally Twice-daily to Patients with Alcoholic Hepatitis (Protocol DS102A-05-AH1 – Pilot Phase, Day 0)

Figure 3 Individual Subject-overlays Plasma Free 15(S)-HEPE Concentrations (ng/ml) versus Time (linear and semilogarithmic scales) for 1000 mg BD DS102 Administered Orally Twice-daily to Patients with Alcoholic Hepatitis (Protocol DS102A-05-AH1 – Pilot Phase, Day 7)

Figure 4 Individual Subject-overlays Plasma Total 15(S)-HEPE Concentrations (ng/ml) versus Time (linear and semilogarithmic scales) for 1000 mg BD DS102 Administered Orally Twice-daily to Patients with Alcoholic Hepatitis (Protocol DS102A-05-AH1 – Pilot Phase, Day 7)

Figure 5 Individual Subject-overlays Plasma Free 15(S)-HEPE Concentrations (ng/ml) versus Time (linear and semilogarithmic scales) for 1000 mg BD DS102 Administered Orally Twice-daily to Patients with Alcoholic Hepatitis (Protocol DS102A-05-AH1 – Pilot Phase, Trough Concentrations)

Figure 6 Individual Subject-overlays Plasma Total 15(S)-HEPE Concentrations (ng/ml) versus Time (linear and semilogarithmic scales) for 1000 mg BD DS102 Administered Orally Twice-daily to Patients with Alcoholic Hepatitis (Protocol DS102A-05-AH1 – Pilot Phase, Trough Concentrations)

APPENDICES
App Fig 1-6

Individual Plasma Free 15(S)-HEPE Concentrations (ng/ml) versus Time (semilogarithmic scale only) and Terminal Phase Regressions, by Subject for 1000 mg BD DS102 Administered Orally Twice-daily to Patients with Alcoholic Hepatitis (Protocol DS102A-05-AH1 – Treatment Phase)

App Fig 7-12

Individual Plasma Total 15(S)-HEPE Concentrations (ng/ml) versus Time (semilogarithmic scale only) and Terminal Phase Regressions, by Subject for 1000 mg BD DS102 Administered Orally Twice-daily to Patients with Alcoholic Hepatitis (Protocol DS102A-05-AH1 – Treatment Phase)

DATA DISPLAYS FOR TREATMENT STUDY-PHASE (prepared separately)

Figure x1 Mean (+/-SD) Plasma Free 15(S)-HEPE Concentrations (ng/ml) versus Time (linear and semilogarithmic scales) for 1000 mg BD DS102 Administered Orally Twice-daily to Patients with Alcoholic Hepatitis (Protocol DS102A-05-AH1 – Treatment Phase)

[figure not shown]
Figure x2 Mean (+/-SD) Plasma Total 15(S)-HEPE Concentrations (ng/ml) versus Time (linear and semilogarithmic scales) for 1000 mg BD DS102 Administered Orally Twice-daily to Patients with Alcoholic Hepatitis (Protocol DS102A-05-AH1 – Treatment Phase)

Figure x3 Individual Subject-overlays Plasma Free 15(S)-HEPE Concentrations (ng/ml) versus Time (linear and semilogarithmic scales) for 1000 mg BD DS102 Administered Orally Twice-daily to Patients with Alcoholic Hepatitis (Protocol DS102A-05-AH1 – Treatment Phase)

Figure x4 Individual Subject-overlays Plasma Total 15(S)-HEPE Concentrations (ng/ml) versus Time (linear and semilogarithmic scales) for 1000 mg BD DS102 Administered Orally Twice-daily to Patients with Alcoholic Hepatitis (Protocol DS102A-05-AH1 – Treatment Phase)

[figure not shown]
PK Model Data Displays - FIGURES
Study DS102A-05-AH1
Pilot and Treatment Phases
PKPD# Afm091318a

A Free
B Total

[figure not shown]
Note: Data below for plotting, not for printout

Time (hr)	Day 0	Day 7
0		
0.5		
1	17	29
2	900	1555
3	1800	3110
4	2400	4147
6	1100	1901
7	600	1037
8	390	674
10	350	605
12	330	570

PK Mock Data Displays - FIGURES
Study DS02A-05-AH1
Pilot and Treatment Phases
PKPD# Afm091318a

C Free
D Total

[figure not shown]
[figure not shown]

Note: Data below for plotting, not for printout

Time (day)	Day 0
0	250
0.5	250
3	300
5	320
7	330
14	330
21	330
28	330

PK Mock Data Displays - FIGURES
Study DS02A-05-AH1
Pilot and Treatment Phases
PKPD# Afm091318a

- 1** Free, Day 0
- 2** Total, Day 0
- 3** Free Day 7
- 4** Total, Day 7

[figure not shown]
[figure not shown]

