## 1.6 Previous Clinical Safety Studies with 15(S)-HEPE

The company sponsored a phase I study, DS102A-01 (EudraCT 2015-001153-33), a first in man study conducted in healthy volunteers, to assess the safety, pharmacokinetics and effect of food on orally administered DS102. DS102 (15(S)-HEPE EE) was administered to healthy volunteers in the following regimens: a single dose of 100mg, 500mg, 1000mg, or 2000mg under fasted conditions; a single 500mg dose under two fed conditions (standard diet and high fat diet); and as multiple doses of 500mg, 1000mg or 2000mg taken once daily for 28 consecutive days in a fasted state. In this study, 57 subjects (male and female) aged 18 to 45 years were enrolled with eight subjects (at least three males and three females per cohort) in each cohort. Subjects in each cohort were randomised in a ratio of 3:1 to receive either DS102 or placebo. Cohorts were commenced in a sequential manner starting with the 100mg, 500mg and 1000mg single dose cohorts in parallel and progressing to higher doses and multiple doses following evaluation by a safety monitoring committee (SMC).

This first in man study showed that DS102 overall had an excellent safety profile, a short elimination half-life of approximately two hours and a  $T_{max}$  of approximately four to eight hours. Results across dose levels studied showed high variability in the single and multiple dose cohorts and did not show a linear correlation between increasing dose and that of systemic exposure. The study demonstrated that administration with food increased the bioavailability of 15(S)-HEPE, as mean plasma concentrations of 15(S)-HEPE were higher under fed conditions compared to fasted conditions. There was no difference in bioavailability between normal and high fat diet fed conditions. DS102 was safe and well-tolerated in healthy subjects in this study with no serious adverse events (SAEs) reported.

The company is currently recruiting patients for two phase II studies, DS102A-02 (EudraCT 2016-000311-33), to assess the safety and efficacy of orally administered DS102 in NAFLD patients at doses of 1000mg or 2000mg per day, with placebo as a comparator and DS102A-03 (EudraCT 2016-002853-39), to assess the safety and efficacy of orally administered DS102 in COPD patients at doses of 1000mg or 2000mg per day, with placebo as a comparator. To date, DS102 has been well-tolerated with no related SAEs reported.

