### *Pharmacokinetic Objective:*

- To evaluate the PK of 15(S)-HEPE following orally administered DS102 capsules, in six adult patients with severe acute decompensated AH in an initial pilot phase of the study, followed by trough level assessment of 15(S)-HEPE in all study participants.

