6.3 General Derivations

- Definition of baseline

Baseline is defined as the last non-missing value (including scheduled and unscheduled assessments) prior to the patient receiving study treatment.

- Incomplete dates

For calculation purposes, incomplete dates will be completed using worst case. Further details are detailed in the relevant sections as required.

- Non-numeric values recorded in a numeric field

In the case where a variable is recorded as “>x”, “ $\geq x$ ”, “ $<x$ ” or “ $\leq x$ ” in a numeric field, then for analysis purposes a value of x will be taken. Where a range of values is quoted the midpoint of the range will be taken. For example, if a laboratory safety parameter is reported as being below the limit of quantification or $< x$, the value of the limit will be used in the calculation of summary statistics. The recorded value will be reported in listings.

- Methods for handling withdrawals and missing data

Imputation of any data will be detailed in the relevant sections.

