Pharmacokinetic (PK) Set (pilot phase) will consist of those patients who have at least one quantifiable post-dose plasma 15(S)-HEPE concentration. Patients will be analysed according to the treatment actually taken. An evaluable profile allows the determination of one or more PK parameters and will be determined at the discretion of the pharmacokineticist. The Pharmacokinetic set will be used for the summaries of all PK data.

The **Pharmacokinetic (PK) Set (double-blind phase)** will consist of those patients who have at least one quantifiable post-dose plasma 15(S)-HEPE concentration. Patients will be analysed according to the treatment actually taken.

The treatment actually taken will assumed to be the treatment randomised to unless otherwise notified by the sponsor at the time of unblinding.

The list of patients included in the SAF, FAS, PPS and PK (pilot phase) and PK (double-blind phase) set will be agreed prior to breaking the blind for blinded studies, once all study data is available. The definitions for the SAF, FAS and PK (pilot phase) and PK (double-blind phase) set are sufficient to determine the patients included within these analysis sets and so do not require listing and agreeing prior to breaking the blind for blinded studies.

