During the study, 8 visits to the clinic are scheduled after the screening visit (Visit 1): one at the start of the comparative treatment period (Baseline/Visit 2) and six in the comparative treatment period (Visit 3/Day 3, Visit 4/Day 5, Visit 5/Day 7, Visit 6/Day 14, Visit 7/Day 21, Visit 8/Day 28 or Early Termination).

Blood samples for PK analysis will be collected via direct venipuncture as per the Study Flow Chart at Visit 2/Baseline, Visit 3/Day 3, Visit 4/Day 5, Visit 5/Day 7, Visit 6/Day 14, Visit 7/Day 21, and Visit 6/Day 28/Early Termination. Trough plasma samples will be obtained from all patients (pilot and double-blind phases) prior to first daily dose on the indicated days. Additional post-dose serial plasma samples will be obtained from the 6 patients of the Pilot phase for full PK characterization on Days 0 and 7 at 0.5, 1, 2, 3, 4, 6, 7, 8, 10, and 12 (before next dose) hours post-dose. A 1 mL blood sample will be taken at each time point. Following centrifugation, plasma samples will be split in two and a back-up sample will be handled as described in the laboratory manual.

Plasma free and total 15(S)-HEPE concentrations will be determined by Charles River Laboratories (Edinburgh Ltd) using validated liquid chromatography tandem mass spectrometry (LC-MS/MS) methods.

Input Data Handling

Evaluability Criteria

The **Pharmacokinetic (PK) Set** will consist of those patients who have at least one quantifiable post-dose plasma 15(S)-HEPE concentration. Patients will be analysed according to the treatment actually taken. An evaluable profile allows the determination of one or more PK parameters and will be determined at the discretion of the pharmacokineticist. The Pharmacokinetic set will be used for the summaries of all PK data.

Off-time Sample Times

Actual sampling times will be used for all analyses. Nominal time will be used to tabulate plasma 15(S)-HEPE concentrations by time and for all figures.

Out of Range Data

Plasma 15(S)-HEPE concentration-time data will be reviewed to confirm all reported values are valid and are within the lower and upper limits of assay quantitation. Values below or above these limits will be identified as BLQ and ALQ, respectively. BLQ values will be treated either as zero for concentrations prior to the first Cmax or as missing values in all other pharmacokinetic analyses and data presentations. ALQ values will be treated as missing in all analyses and presentations.

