Where feasible, the following non-compartmental PK parameters will be generated:

Parameter	Definition	Units	Precision
%Extrap	Percentage of AUC_{inf} obtained by extrapolation	%	1 dp
AUC_{inf}	Area under the plasma concentration-time curve from time 0 extrapolated to infinite time	ng•hr/mL	1 dp
AUC_t	Area under the plasma concentration-time curve from time 0 to the time of the last quantifiable concentration	ng•hr/mL	1 dp
AUC_{tau}	Area under the plasma concentration-time curve over a dosage interval	ng•hr/mL	1 dp
C_{avg}	Average plasma concentration over a dosage interval	ng/mL	3 dp
C_{last}	Last quantifiable plasma concentration	ng/mL	3 dp
C_{max}	Maximum observed plasma concentration	ng/mL	3 dp
Flucp	Fluctuation at pharmacokinetic steady-state	%	1 dp
K_{el}	Apparent first-order terminal elimination rate constant	1/hr	4 dp
R_{ac}	Accumulation ratio at pharmacokinetic steady-state	%	1 dp
$t_{1/2}$	Apparent first-order terminal elimination half-life	hr	1 dp
t_{last}	Time to reach the last quantifiable plasma concentration	hr	1 dp
t_{max}	Time of maximum observed plasma concentration	hr	1 dp
t_{ss}	Time to achieve pharmacokinetic steady state	hr	1 dp

Planned Statistical Assessments

Descriptive statistics will be used to summarize plasma free and total 15(S)-HEPE concentrations and resultant pharmacokinetic parameters by treatment across study subjects. Summary statistics will include number of non-missing observations, geometric mean, mean, standard deviation, coefficient of variation, minimum, median, and maximum as appropriate.

Analysis Output/Summarization

Data displays for patients from the pilot phase and the double-blind phase of the study will be presented separately. Should the study be discontinued after the pilot phase, the listings described in the sections below will be produced for the pilot phase only.

Summarization

Pharmacokinetic analysis methods, results, and conclusions will be summarized in a separate PK Report, with pertinent information included in the clinical study report. Results for plasma 15(S)-HEPE concentrations and 15(S)-HEPE pharmacokinetic parameters will be summarized and discussed relative to differences between treatments and prior study results. Conclusions related to the study objectives will be presented.

Datasets

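### Trough levels below the quantification limit are set to missing in summaries as well as in curve fitting, so any that occur bias the reported trough means upward; the SAP also carries a second, different rule.

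*SAP*

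**What the plan says.** - **Objective.** Protocol section 4 asks for full PK in six pilot patients, "followed by trough level assessment of 15(S)-HEPE in all study participants". SAP Appendix 1 (the PK data analysis plan, PKAP), Sampling Design, says: "Trough plasma samples will be obtained from all patients (pilot and double-blind phases) prior to first daily dose on the indicated days".
- **BLQ rule.** PKAP, Out of Range Data: "BLQ values will be treated either as zero for concentrations prior to the first Cmax or as missing values in all other pharmacokinetic analyses". The sentence then extends to data presentations. Values above the upper limit are also dropped: "ALQ values will be treated as missing in all analyses and presentations".
- **Summaries.** PKAP, Planned Statistical Assessments: "Summary statistics will include number of non-missing observations, geometric mean, mean, standard deviation, coefficient of variation, minimum, median, and maximum as appropriate". The mock trough tables have rows for these statistics and none for a BLQ count.
- **Who is included.** SAP 6.4 and the PKAP require "at least one quantifiable post-dose plasma 15(S)-HEPE concentration" for the PK Set. Protocol 12.6 defines the PK population as all patients who received at least one dose. SAP 6.25, which lists changes from the protocol, does not mention this narrowing.
- **A different rule.** Under SAP 6.3, for a result below the limit of quantification, "the value of the limit will be used in the calculation of summary statistics".
- **Reach.** SAP 6.15 sends the PK analyses of both phases to Appendix 1. The Scope paragraph of Appendix 1 covers the pilot phase and places preparation of the treatment-phase displays outside the PKAP.

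**The concern.** Setting late BLQ values to missing is reasonable when estimating a terminal slope. It is not neutral in a table of trough levels, because a BLQ result is a measured low value, not an absent one. Deleting it makes the table describe only the samples that were quantifiable. Because the tables give n of non-missing values and no BLQ count, a reader of the summary cannot tell a low trough from an uncollected one.

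Trough assessment in all participants is the PK objective of the randomised phase. SAP 6.25 drops the protocol's PK parameters for that phase, so the concentration summaries are its only remaining PK output. With two below-limit rules and an unclear scope, two programmers could produce different double-blind trough tables from the same data.

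**Working it through.** The documents give no lower limit of quantification (LLOQ), BLQ fraction or coefficient of variation, so there is no plan figure to reproduce. The direction follows from the text; the size is illustrative.

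**Which troughs are affected.** If the first Cmax means the peak after the first dose, all troughs from Day 3 on come later and a BLQ value becomes missing. A BLQ Day 0 pre-dose sample, which has a column in the mock trough table, becomes zero. If Cmax is read per profile, a BLQ pre-dose value on pilot Day 7 would also become zero, which pulls that visit's mean down. Double-blind patients have trough samples only, so no Cmax is observed for them. The term is not defined for either case.

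**Bound without a distribution.** Let f be the BLQ fraction at a visit and m the mean of the quantifiable values. Each BLQ value lies between 0 and the LLOQ, so the true mean lies between (1-f)m and (1-f)m + f x LLOQ. The reported mean is m. It is therefore too high by a factor above 1 and at most 1/(1-f):
- f = 10%: 1/0.90 = 1.11
- f = 1/6 (one of six pilot patients): 1/(5/6) = 1.20
- f = 20%: 1/0.80 = 1.25
- f = 50%: 1/0.50 = 2.00

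This bound is for the arithmetic mean only.

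**Log-normal illustration (assumed).** With sigma = sqrt(ln(1 + CV^2)) and z = Phi^-1(f):
- mean ratio, reported to true = Phi(sigma - z)/(1-f)
- geometric mean ratio = exp(sigma x phi(z)/(1-f))

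Example, CV 100% and f = 20%: sigma = 0.833 and z = -0.842. The mean ratio is 0.953/0.80 = 1.19. The geometric mean ratio is exp(0.833 x 0.280/0.80) = 1.34.

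Ratios to the true value at f = 20%, by BLQ rule:

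| Assumed CV | Missing: mean | Missing: geo. mean | Limit (SAP 6.3): mean | Limit: geo. mean | LLOQ/2: mean | LLOQ/2: geo. mean |
|---|---|---|---|---|---|---|
| 50% | 1.132 | 1.180 | 1.026 | 1.054 | 0.966 | 0.918 |
| 100% | 1.191 | 1.338 | 1.023 | 1.097 | 0.988 | 0.955 |
| 150% | 1.216 | 1.462 | 1.018 | 1.129 | 0.995 | 0.983 |

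Under the missing rule, over the same CV range, f = 10% gives a mean ratio of 1.07-1.10 and a geometric mean ratio of 1.10-1.24. At f = 50% they are 1.36-1.72 and 1.46-2.38.

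**Are low troughs plausible?** Protocol 1.6 reports "a short elimination half-life of approximately two hours" and a Tmax of about four to eight hours, in healthy volunteers. Assuming mono-exponential decline from the peak, the fraction of peak left at 12 h is 2^(-(12-4)/2) = 6% to 2^(-(12-8)/2) = 25%. Low troughs are plausible; whether they fall below the LLOQ cannot be determined.

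**PK Set.** Once BLQ values are missing, excluding an all-BLQ patient hardly moves the mean, since that patient contributes no on-treatment value. The exclusion matters for the denominator: a BLQ count taken on the PK Set would miss exactly the patients with the lowest levels.

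**The case against.** The strongest reply is that BLQ troughs may hardly occur. Protocol 1.3 calls the compound endogenous, the PKAP has a paragraph on detectable pre-dose concentrations, and the placeholder plotting data show no BLQ trough. With none, the bias is zero. This stands: the effect is conditional and its size unknown.

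Second, the missing rule may not govern double-blind troughs at all, given the PKAP's scope note. Under the SAP 6.3 rule the mean in the illustration is overstated by only about 2-3% at 20% BLQ. This also stands, though SAP 6.15 points the other way, the example in SAP 6.3 is a laboratory safety parameter, and the unresolved conflict is itself part of the point.

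Third, a reader might infer that the rule hides missed doses or poor absorption. The documents do not support that. SAP 6.10 summarises compliance and lists diary, dispensing and return data; the PKAP flags out-of-range values as BLQ, plans individual concentration tables and delivers a concentration dataset. What is lost is visibility in the summary tables.

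Fourth, a reader might infer that the Data and Safety Monitoring Board's pilot review is undermined. That review also has full Day 0 and Day 7 profiles. Cmax is unaffected, and AUC should change little because only low late values are lost.

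Setting above-limit values to missing biases in the opposite direction, but is unlikely to matter at trough.

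**Conclusion.** The point holds as a conditional one, and it is minor. Followed as written, the PKAP rule raises the trough mean and geometric mean whenever a BLQ trough is dropped. The mean is overstated by at most 1/(1-f), or 1.20 for one of six pilot patients. At 20% BLQ and an assumed log-normal with CV 50-150%, the overstatement is about 13-22% for the mean and 18-46% for the geometric mean. This rests on reading the first Cmax as the peak after the first dose and on BLQ rates and CVs that the documents do not give.

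The documents do not support a flat statement that the trial's exposure will be overstated: no LLOQ or BLQ rate is given, and only trough summaries are involved. Two things hold whatever the BLQ rate: the below-limit rules and their scope are not reconciled within the SAP, and the PK Set is narrower than Protocol 12.6 without being declared in SAP 6.25. The summaries are descriptive, and the primary MELD analysis is untouched.

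**What to change.** Amend the PKAP and the SAP as follows.
- State one BLQ rule for trough tables and figures in both phases that keeps BLQ troughs in the summary: for example LLOQ/2, or the limit as in SAP 6.3, with median and range alongside. Say explicitly that it takes precedence for PK concentrations, and align SAP 6.3, SAP 6.15 and the PKAP Scope paragraph with it.
- Report the number and percentage BLQ by visit and arm.
- Include all treated patients with at least one valid post-dose sample, and record any remaining difference from Protocol 12.6 in SAP 6.25.
- Define the first Cmax for the Day 7 profile and for patients with troughs only.
- Limit the missing rule to terminal-phase estimation.

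The cost is wording and one extra row per trough table, with no new samples or assays. If BLQ values prove rare, the added row documents that.
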